Aim 2a: Determine the effect of early combined EN + PN on intestinal barrier function in children with AHRF.

Aim 2b: Identify patient, disease, and treatment factors, which act as effect modifiers for non-invasive markers of intestinal barrier function for children with AHRF.

Aim 2c: (Exploratory) Determine the influence of EN +/- PN on the intestinal microbiome in children with AHRF.

This proposal is innovative, because will evaluate the extent to which early combined enteral and parenteral nutrition improves delivery of daily and cumulative goal calories, protein, and indices of nutrition (Aim 1), while monitoring for potential negative consequences of early PN on intestinal barrier function (Aim 2). *This proposal is significant*, because it is expected to improve our understanding of optimal timing for parenteral nutritional support and define the effect of route and dose of nutrition, patient, disease, and treatment characteristics on intestinal barrier function. By understanding how patient, disease, and treatment factors impact intestinal barrier function during pediatric AHRF, we may be able individualize dose of enteral nutrition to protect against gut barrier dysfunction and promote new strategies to reduce septic morbidity; meeting the goals of NIH Healthy People 2020.

Timeline of Interventions

Screening and Eligibility

Screening is to take place twice daily (~8am and ~5pm) for newly intubated patients that meet inclusion criteria. All screened patients will receive a study ID. Enter the patient on the SUPPER Enrollment log for study ID. Complete the SUPPER Screening form for all screened patients. If the patient does not meet eligibility, complete the SUPPER Enrollment log and the Supper Screening form and place the Screening form in the study binder under Completed Screenings. If the patient meets all inclusion criteria, with no exclusion criteria, the patient is eligible and the family may be approached for consent. If unsure whether an individual patient can be enrolled in the SUPPER study, please call the University of Arizona PI.

Inclusion Criteria-

Intent: To identify PICU patients who have Acute Hypoxemic Respiratory Failure and who will receive early enteral feeding.

Inclusion Criteria

1. Admitted to study hospital pediatric intensive care unit (PICU),
2. One month to 16 years of age,
3. Exhibits Acute Hypoxemic Respiratory Failure as defined as:

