Each successfully enrolled and randomized patient will have a patient study file. This file will contain all forms for that patient. SUPPER Study Sample Kits have been provided for the collection of blood, and stool for this study. One kit is to be used per patient.

Early Parenteral Nutrition Supplementation (EPN)

Supplies, Medications, and Forms to have on hand when starting:

SUPPER Tablet with SUPPER Titration

Supplemental PN (Baxter Clinimix for patients 1 year of age and older; in-house custom PN for infants 1 month and <1 year)

SUPPER Patient Study Binder

SUPPER Sample Kit

Tape measure to perform mid upper arm circumference

Once randomized to Early Parenteral Nutrition (EPN), patients are to be started on the PN intervention within 2 hours of randomization. Patients randomized to EPN will receive enteral nutrition with supplemental PN for 168 hours. Calorie goal and titration of PN/IL are according to the SUPPER Titration Tool. **If at any point the clinical team feels that it is unsafe to continue PN, discontinue PN immediately and record this as a protocol violation. Ensure appropriate monitoring of blood glucose after abrupt discontinuation of PN.** Reducing the hourly rate of PN to achieve clinically indicated fluid restriction is also acceptable for the study protocol. All attempts should be made, and the study protocol is designed to avoid fluid overload as a result of PN. The SUPPER Titration Tool does not allow PN to exceed MIVF rates. Obtain mid upper arm circumference.

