Aim 2. We will assess differences between FABP2, claudin 3, citrulline, lactulose/mannitol ratios, and by study arm. Descriptive plots: serum biomarker (y-variable) over time (x-variable) will be fit, with linear and smoothing splines. Plots are qualitative. Splines allow examination of possible nonlinear relationships and can be used to specify nonlinear or change-point models. We utilize one-way repeated measures ANOVA with the intestinal barrier assays as continuously measured outcomes and time (1,2,3,5, and 7 days) as explanatory variables. If the slope of the serum biomarkers is linear, then change in the slope over time will be calculated using a linear mixed effects model with an AR(1) variance-covariance structure. The variance-covariance structure allows for measurements taken closer together to be more similar than those farther apart in time, and adjusts the standard errors for this correlation. If the relationship between the serum biomarker is not linear in time, then change-point or nonlinear mixed effects models will be used. Aim Multivariable regression analysis will evaluate possible effect modification, or mediation, for non-invasive measures of intestinal epithelial barrier function. Effect modifiers are the interactions with PN group; mediators are those variables that could have a potential additive effect with the PN group. Additionally we will assess any potential confounding that might be present by assessing the change in the parameter estimate for the PN group effect. Potential modifiers, mediators, and confounders, include clinical variables, center effects, and severity of illness. We will test associations between measures of intestinal function and clinical variables, severity of illness, as well as dose and route of nutrition. With 40 subjects total, we will be able to include up to 4 possible predictors; therefore, if effect modifiers are warranted, model simplification will be necessary. If the study is stopped early the analysis plan may be modified due to small sample size.

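### Aim 2a is a between-arm question, but the only test named for the serial biomarkers has time as its sole factor, and no fully specified test compares the arms

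*Combined protocol and SAP*

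**What the plan says.** Aim 2a in the Project Summary is comparative: "Determine the effect of early combined EN + PN on intestinal barrier function in children with AHRF". The Aim 2 paragraph of the Statistical Analysis Plan opens in the same spirit, "We will assess differences between FABP2, claudin 3, citrulline, lactulose/mannitol ratios, and by study arm", but that sentence names no test.

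The analysis is then described in this order:

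- Descriptive plots of each biomarker over time.
- The named test: "We utilize one-way repeated measures ANOVA with the intestinal barrier assays as continuously measured outcomes and time (1,2,3,5, and 7 days) as explanatory variables".
- Mixed models. For a linear course, "change in the slope over time will be calculated using a linear mixed effects model with an AR(1) variance-covariance structure". Otherwise, change-point or nonlinear mixed models.
- A multivariable regression on modification, mediation and confounding. Here treatment group appears: "Effect modifiers are the interactions with PN group", and confounding is judged by "assessing the change in the parameter estimate for the PN group effect".

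The Aim 1 paragraph, by contrast, names a two-sample t test between arms and a 0.05 threshold. The Aim 2 paragraph gives neither a between-arm test for the serial biomarkers nor an alpha.

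**The concern.** A one-way repeated measures ANOVA on time asks whether the mean over all patients changes across the sampling days. It cannot say whether early PN changed that course. Critically ill children may well show biomarker changes during the first week whatever the feeding strategy, so a significant result could be taken as an answer to Aim 2a when it is not one.

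The mixed models would be the natural place for the arm comparison. They do not exclude arm, but they do not state it either. The regression that does contain treatment group gives no outcome time, no handling of repeated measures, no use of the hour-0 value, no stated hypothesis and no alpha. The analyst would have to choose the model, contrast, time points and baseline handling with the data in hand. The plan already lets the observed curves decide the model form, which makes a contrast fixed in advance more important.

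**Working it through.** The plan states no power or sample size figure for Aim 2, so there is none to reproduce. The check has two parts.

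**1. Where arm appears.**

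| Element of the Aim 2 plan | Explanatory terms stated | Arm stated? |
|---|---|---|
| Opening sentence | none (intent only) | yes, no test |
| Repeated measures ANOVA | time | no |
| Linear mixed model, AR(1) | time (slope) | no |
| Change-point or nonlinear mixed model | time | no |
| Multivariable regression | PN group, interactions, clinical variables, centre, severity | yes, but no outcome time, repeated-measures handling, hypothesis or alpha |

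**2. What the ANOVA responds to.**

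*Inputs from the documents.* The total comes from "With 40 subjects total, we will be able to include up to 4 possible predictors". The draw times (0, 12, 24, 48, 72, 96, 120, 144, 168 h) come from the sampling tables in the EPN and LPN sections.

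*Assumed inputs, not in the documents.* 20 per arm, unit SD, correlation rho^(days apart) with rho = 0.3/0.5/0.7/0.9, complete data, two-sided 5%, Greenhouse-Geisser correction. Results are listed in the order of rho.

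*Comparator.* Each patient's mean over 12, 24, 48, 72 and 96 h, regressed on arm and the hour-0 value.

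The ANOVA statistic is F = MS(time)/MS(error). Its numerator depends only on the pooled means, m(t) = [early(t) + late(t)]/2 with equal arms.

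- **Both arms rise linearly by 1 SD over 168 h, no arm effect.** At 24, 48, 72, 120 and 168 h, m(t) = t/168 = 0.14, 0.29, 0.43, 0.71, 1.00. The ANOVA rejects 94/94/96/100%; the arm contrast rejects 5/5/5/5%.
- **Arms diverge symmetrically to a 1 SD gap by 48 h.** m(t) = (+d/2 − d/2)/2 = 0 at every time. The ANOVA rejects 4/4/5/4%; the arm contrast rejects 98/97/96/100%.

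Both ANOVA results hold whichever hours the listed days denote: about 94 to 100% and about 3 to 5%.

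**The day list.** Days 1, 2, 3, 5, 7 could mean 24, 48, 72, 120, 168 h (reading A). The Daily Data Collection text, which has a Day 0 followed by a Day 1, supports this. They could also mean 0, 24, 48, 96, 144 h (reading B). The EPN and LPN sections, which treat the first 24 hours as preceding study day 2, allow this. Both sets are scheduled draws. If only one arm changes, the result depends on the reading:

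| One arm changes by 1 SD | m(t), A | ANOVA rejects, A | m(t), B | ANOVA rejects, B |
|---|---|---|---|---|
| by 24 h, then constant | 0.5, 0.5, 0.5, 0.5, 0.5 | 5/5/4/5% | 0, 0.5, 0.5, 0.5, 0.5 | 57/61/71/99% |
| linearly by 48 h, then constant | 0.25, 0.5, 0.5, 0.5, 0.5 | 15/16/19/38% | 0, 0.25, 0.5, 0.5, 0.5 | 55/58/66/94% |

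Even where the ANOVA rejects, it cannot attribute the change to an arm.

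**Value of the hour-0 sample.** The variance of the 12–96 h mean is 0.351/0.476/0.643/0.865 unadjusted and 0.313/0.368/0.371/0.211 given hour 0. The reduction is 1 − 0.313/0.351 = 11% at rho 0.3 and 1 − 0.211/0.865 = 76% at rho 0.9.

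**The case against.** The best defence is that the ANOVA was never offered as the Aim 2a test. The paragraph opens with a by-arm intent and moves from plots to a time-course test, to mixed models, to a regression. Judging confounding by the shift in a treatment-group estimate presupposes a fitted model with arm in it. Read that way, the ANOVA is a descriptive step, and the percentages above only show that a test of time tests time.

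Much of this stands. A reader might infer that arm is absent from the Aim 2 analysis; that goes too far, because the intent is stated and a treatment-group parameter is implied. The defence does not supply the missing test, though. No sentence says which model, time points, baseline handling or alpha will decide Aim 2a. The pilot label does not excuse this either, since only Aim 2c is marked exploratory.

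Two other inferences are tempting:

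- *That the ANOVA misses changes one arm has made by 24 h, and leaves out hours 0 and 96.* Both hold on reading A and fail on reading B. The documents do not settle which is meant.
- *That the rejection rates forecast what this trial would gain or lose.* They rest on assumed correlations, effect sizes and complete data. Blood is drawn only from catheters placed for clinical care, so missed draws are likely and the comparator's 96 to 100% is a best case.

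**Conclusion.** The point stands as a gap in specification that should be fixed. The only named test for the serial biomarkers cannot answer Aim 2a, the mixed models name no arm term, and the regression that contains treatment group is not specified well enough to serve. On the assumed inputs the ANOVA would nearly always reject with no arm effect and a common 1 SD rise, and would reject at about its nominal level when the arms diverge symmetrically to a 1 SD gap. The conclusion itself needs none of those inputs; it follows from the factors named in the plan. What the ANOVA does with a change in one arm only remains open until the day list is stated in hours. The scheduled samples can support a between-arm test, so the gap lies in the analysis text and not in the design.

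**What to change.** For each serial blood biomarker, replace the time-only ANOVA with the mixed model that the plan already names, and write its terms out before the data are analysed by arm:

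- **Terms:** arm, categorical time in hours, arm-by-time, and the hour-0 value as covariate, with a correlation structure based on elapsed time because the draws are unequally spaced.
- **Test:** name one between-arm contrast as the Aim 2a test, with its alpha. An example is the arm difference averaged over the 12, 24, 48, 72 and 96 h draws.
- **Window:** treat later draws as secondary. In the early arm, "Patients randomized to EPN will receive enteral nutrition with supplemental PN for 168 hours", while PN in the late arm may begin at hour 96, so later samples can mix the two strategies. Flag hour-96 samples drawn after late PN has started.
- **Clock:** define one analysis time origin for both arms, such as randomization. The EPN section counts from the start of PN. The LPN section counts from the start of enteral feeds, which may come before randomization. Record whether EN was running at hour 0.
- **Days:** state the analysis times in hours.

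The cost is SAP wording, a few more model terms and possibly assays of draws already scheduled. With five post-baseline draws the model has 1 + 4 (time) + 1 (arm) + 4 (arm-by-time) + 1 (hour 0) = 11 fixed effects. The gain in precision from hour 0 depends on a correlation that the documents do not give. Naming a primary biomarker or a multiplicity rule is optional and separate from this point.

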To assess 28 Day Vitals first check to see if the patient is still hospitalized or if the patient died while hospitalized. If patient is not hospitalized, use the SUPPER Contact form to contact the patient's parents/guardians. Three attempts should be made to contact the parents/guardians. If the third attempt is unsuccessful, attempt to contact the patient's primary care physician. If the patient has not

been seen by the primary care physician since hospitalization, assess vital status from county death records. If you can successful contact either the patient's parents/guardians or primary care physician obtain information on whether the patient's condition is better, the same, or worse from condition at discharge. Also obtain information on whether the patient was readmitted to the hospital on or before 28 Days.

Late Parenteral Nutrition Supplementation (LPN)

Supplies and forms for have on hand after randomization.

SUPPER Tablet with SUPPER Titration

SUPPER Patient Study Binder

SUPPER Sample Kit

Tape measure to measure mid upper arm circumference

Once randomized to Late Parenteral Nutrition (LPN), patients are to be started on EN within 2 hours of randomization if not already started. Patients randomized to LPN will receive enteral nutrition for 168 hours and supplemental PN if not reaching 80% goal feeds starting at Hour 96 for a total of 72 hours. Calorie goal and titration of feeds are according to the SUPPER Titration. Obtain mid upper arm circumference.

Prior to LPN Hour 0, set up SUPPER Tablet at bedside. Open the SUPPER Titration and enter all of the patient demographics, formula, and fluid information at the top. Rates for EN and remaining fluids will populate. Print SUPPER Titration for bedside and study binder and review with the bedside nurse.

The SUPPER Titration uses Schofield's equation to calculate the initial kcal/day goal. Patients are to initially receive a max of 75% of calorie goal and 1.5gm/kg/day protein for the first 24 hours. Patients will receive 100-120% of MREE and 2-3gm/kg/day protein with combined EN by study day 2, not to exceed 1600mL/M²/day in fluids. As the patient can tolerate, EN is to be escalated every 4 hours to full kcal/day goal.

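### Aim 2 fixes no arm contrast for intestinal barrier function, and a single slope to day 7 can attenuate or miss an early PN effect

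*Combined protocol and SAP*

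**What the plan says.** Statistical Analysis Plan, Aim 2, sets out to compare the barrier markers by study arm. The steps it then describes are these:

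- Descriptive plots with linear and spline fits. On these it says "Plots are qualitative" and "Splines allow examination of possible nonlinear relationships and can be used to specify nonlinear or change-point models".
- A one-way repeated measures ANOVA with "time (1,2,3,5, and 7 days) as explanatory variables". Study arm is not named as a factor.
- A mixed model with AR(1) covariance, whose form depends on the data: "If the slope of the serum biomarkers is linear, then change in the slope over time will be calculated". For the other case the text reads: "If the relationship between the serum biomarker is not linear in time, then change-point or nonlinear mixed effects models will be used".
- A multivariable regression in which a PN group effect and interactions with PN group appear, with no time point or window attached.

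The section gives no criterion for linearity, no knot, no arm-by-time term in the longitudinal model, no 0-hour covariate and no primary time point.

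On design, the early arm has supplemental PN over 168 hours, reduced as enteral feeding advances. The late arm receives "supplemental PN if not reaching 80% goal feeds starting at Hour 96 for a total of 72 hours" (Late Parenteral Nutrition Supplementation). The sampling tables in both arm sections schedule blood at 0, 12, 24, 48, 72, 96, 120, 144 and 168 h.

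**The concern.** Aim 2a asks what early combined feeding does to barrier function. By design the arms differ in PN exposure mainly up to hour 96. After that, late-arm children below the feeding threshold also receive PN, so a difference that has built up may level off or shrink. A straight line to day 7 averages the two periods, and its slope need not describe the early one.

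Whether a slope is the tested quantity at all is settled only after looking at the data, so two analysts following the same plan could report different estimates. Samples that would help are also not clearly used. Five days are listed against nine scheduled draws, so four draws are left out under either day numbering. They include 96 h if day 5 means 120 h. At stake is a pilot that reports little or no barrier effect when one was present early, or an effect whose definition came from the data.

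**Working it through.** The plan gives no effect size, SD or power for Aim 2, so there is no figure to reproduce. Its only related number is 4 predictors for 40 subjects (40/4 = 10 each).

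**Inputs from the documents.** Draw times: the sampling tables (nine draws; the Sample Collection section speaks of a maximum of 11, and the tables are used here). Listed days 1, 2, 3, 5, 7: SAP Aim 2. Late PN from hour 96: LPN section. Total of 40 subjects: SAP Aim 2.

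**Assumed.** The arm gap g(t) is t/4 up to day 4 (0.25 units/day, peak 1). By day 7 it then falls to 0, falls to 0.5, or stays at 1.

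**Step 1: least-squares slope of the gap.** b = Σ(t − t̄)g / Σ(t − t̄)².

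*Listed days as 24, 48, 72, 120, 168 h.* t̄ = 18/5 = 3.6; deviations −2.6, −1.6, −0.6, 1.4, 3.4; Σ(t − t̄)² = 23.2. Days 1-3 contribute −2.6(0.25) − 1.6(0.5) − 0.6(0.75) = −1.90.
- Closes: g(5) = 0.667, g(7) = 0. (−1.90 + 0.933)/23.2 = −0.042.
- Halves: g(5) = 0.833, g(7) = 0.5. (−1.90 + 1.167 + 1.70)/23.2 = +0.042.
- Plateaus: (−1.90 + 1.40 + 3.40)/23.2 = +0.125.

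*All nine draws.* t̄ = 28.5/9 = 3.167; Σ(t − t̄)² = 140.25 − 90.25 = 50.0.
- Closes: (12.896 − 3.167 × 3.625)/50 = +0.028.
- Halves: (19.229 − 3.167 × 4.625)/50 = +0.092.
- Plateaus: (25.5625 − 3.167 × 5.625)/50 = +0.155.

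*Listed days with day 1 starting at hour 0* (0, 24, 48, 96, 144 h; same deviations): +0.079, +0.128, +0.177.

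Against the true early slope of 0.25, the plateau case keeps 0.125/0.25 = 50% to 0.155/0.25 = 62%.

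**Step 2: power for the closing gap.** Further assumptions: peak 1 SD, 20 per arm, no dropout, two-sided 0.05, an arm-by-time term in the slope model, and correlation 0.4 + 0.6 × 0.5^(days apart).

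| Estimate | Listed days (24-168 h) | All nine draws |
|---|---|---|
| Straight-line slope gap | 12% (estimate −0.042 SD/day) | 5% (estimate +0.007 SD/day) |
| Mean gap to hour 96 | 44% | 52% |
| Gap at hour 96 | not sampled | 89% |
| Fixed knot at hour 96, 2 df | 68% | not run |

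The slopes here are weighted for the correlation, which is why the nine-draw value differs from step 1. Hour 96: SE = √(2/20) = 0.316, z = 1/0.316 = 3.16, power = Φ(3.16 − 1.96) = 0.885. At a 0.5 SD peak the same calculation gives 35%. Mean gap on days 1-3: 0.5, with SE = √(0.1 × 0.767) = 0.277 and z = 1.81. The hour-96 figure is favourable because the assumed gap peaks there.

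**Step 3: would the fallback be triggered?** The plan gives no test, so a 5% test of curvature stands in for the plots, with the late arm's own trajectory taken as flat (20,000 simulated trials). Share of trials in which the closing gap is still judged linear:

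| Peak | Listed days, pooled / each arm | Nine draws, pooled / each arm |
|---|---|---|
| 0.5 SD | 75% / 53% | 61% / 33% |
| 1 SD | 26% / 4% | 9% / 0.3% |

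**The case against.** Much can be said for the plan, and several stronger readings fail.

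- **An early benefit would be reported with the wrong sign.** A reader might infer this, but the documents do not support it. The day list belongs to the ANOVA sentence; the mixed-model sentence gives no times. For the three shapes above the slope turns negative only if that list is carried over and read as 24-168 h. A different shape, constant to hour 96 and then gone, does give a negative slope on both schedules (-0.19 and -0.06 SD/day). Even so, a negative slope correctly describes a fading difference. It misleads only if read as the direction of the treatment effect, which the SAP does not ask for.
- **Nonlinearity will go unnoticed with 40 children.** Step 3 does not bear this out as a general statement. At a 1 SD peak the fallback is usually triggered. At 0.5 SD it often is not.
- **The plan drops the 96-hour sample.** This depends on day numbering. The daily forms start at Day 0, whereas the feeding targets move from the first 24 hours to study day 2, which suggests that day 1 starts at hour 0. On that reading day 5 is hour 96. Nor is the 96-hour draw reliably free of late PN, given the ±2 h window.
- **Hour 96 is the only valid time point.** Both strategies are defined over 168 h, Aim 2a names no window, late PN is conditional, and full enteral feeding is targeted within 48 hours, so the contrast may narrow sooner. The average to hour 96 has only 44-52% power for the closing shape.
- **Choosing the form inflates type I error.** With a formal curvature gate it is 5.4% in simulation. Values of 9.7% (best-fitting knot) or 11.3% (smallest p) need a search that the plan does not announce, although it does not exclude one.
- **A slope is not always poor.** If the gap plateaus, slope power is 61% on the listed days and 87% on nine draws, despite the attenuated estimate.

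What stands is that the tested quantity is not fixed, and the fallback has no criterion, form or knot.

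**Conclusion.** The point holds as a pre-specification defect with a plausible cost. No stated analysis yields a defined arm difference for Aim 2a, and the form of the longitudinal model is left to qualitative plots. If the arm gap narrows after hour 96, a single slope can miss the early effect (-0.04 to +0.03/day where the early truth is 0.25). If the gap halves the slope is +0.04 to +0.09, and if it plateaus it is +0.125 to +0.155.

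The slope figures rest on the assumed gap shapes. The power and detection figures also rest on the assumed peak sizes, correlations, 1:1 allocation and complete sampling, none of which the documents give. The protection from the fallback depends on effect size and on how many samples are used. The change should be made, but it does not invalidate a pilot.

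**What to change.** Before data are examined by arm, name as the main Aim 2a analysis a mixed model for each serum marker with time as categories, arm, arm-by-time terms and the 0-hour value as covariate, using all scheduled draws. The planned AR(1) structure can stay, written in actual sampling time. Report the arm difference averaged to (or at) hour 96, choosing one in advance, together with the 168-h difference. Keep slope, spline and change-point fits as secondary. State day numbers in hours, and record whether each 96-hour draw came before or after late PN began. The sampling tables give no times for the lactulose/mannitol test, so its contrast needs its own line.

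The cost is SAP wording only: the schedule already provides the samples. The downside is more time parameters. Eight post-baseline times × 2 arms gives 16 means, against 4 for one line per arm, from at most 40 × 8 = 320 values.

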Prior to EPN Hour 0, set up SUPPER Tablet at bedside. Open the SUPPER Titration and enter all of the patient demographics, formula, TPN, and fluid information at the top. Calculate Schofield 100% BMR (height/weight). Rates for EN, PN, Lipids, and remaining available hourly fluids will populate. Print SUPPER Titration for bedside and study binder and review with the bedside nurse. A new SUPPER Titration Tool will need to be created for any change in formula kcal content, calorie goal, or new total fluid order (such as in the case of fluid restriction). As EN feeds are advanced, PN and Lipids decrease. If EN is held or reduced, titrate PN and Lipids according to SUPPER Titration sheet. Choice of PN is based on patient age. If the patient is 1 year of age or older, patients will receive Baxter Clinimix. Patients between 1 month of age and <1 year of age will receive in-house custom PN. The early EN guideline in place for clinical use at CHOP will be used to increase enteral feeds. The goal should be to reach full enteral feeds within 48 hours of initiating EN.

The SUPPER Algorithm uses Schofield's equation to calculate the initial kcal/day goal. Patients are to initially receive a max of 75% of calorie goal and 1.5 gm/kg/day protein for the first 24 hours. Patients will receive 100-120% of MREE (or 100-120% of Schofield predicted BMR in the setting of no MREE) and 2-3gm/kg/day protein with combined PN and EN by study day 2, not to exceed 1600mL/M²/day in fluids (See Table at end of MOO). If there is >20% discrepancy between the unit dietician's usual practice for determination of kcals/day for a given patient and the Schofield predicted BMR, please call the U of A PI to discuss altering the individual patient's kcal goal during the 7-day study intervention. The bedside nurse will titrate PN to maintain calorie goal and protein every 4 hours with the aid of the SUPPER Titration Sheet in place of usual total IVF orders. As patient tolerates increased EN, PN and IL are decreased. In this manner, in the Early PN arm, the patient's delivered calories and protein remain constant, although the route of delivery changes as enteral feeds advance.

	0 Hour	12 Hour	24 Hour	48 Hour	72 Hour	96 Hour	120 Hour	144 Hour	168 Hour
Blood Sample 2mLs	X	X	X	X	X	X	X	X	X
Fecal Samples (if patient has stool)	X		X	X	X	X	X	X	X
Metabolic Cart (REE)	Occurs Between 0 hour and 48 hours (DCMC Only)					Occurs Between 96 hours and 144 hours (DCMC Only)			

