SUPPER Daily Data Collection forms are provided for each of the intervention days and can be found in the patient's study file. For variables with multiple values use value closest to 8:00am, unless otherwise noted. For Day 0 Daily Data Collection, only use post randomization information. These forms do not need to be completed in real time if normal bedside charting clearly provides required information, but we recommend completing them the day after they occur (ex: Day 0 completed on Day 1).

Due to frequent collection of study labs, it is recommended to speak with bedside nurse at these times to gather information about possible adverse events or signs of feeding intolerance. SUPPER study labs may be delayed by 1-2 hours, if necessary, to ensure that blood collection occurs at a time when vasoactive infusions have not been titrated for 1 hour.

Using nutrition charting and tracking of in/out fluids, complete a SUPPER EN/PN Tracking Log for each study day.

Metabolic Cart Testing (University of Arizona only)

Within the first 48 hours of the intervention, the patient's Resting Energy Expenditure (REE) is to be tested using the site's available metabolic cart. Print at least two copies of the REE results; one for the patient study file and one for the patient's medical record. Attending physician caring for the patient should be updated on REE results. Record REE results on the SUPPER Sample log and file in the patient's study file. Repeat REE between Hour 96 and 144 of the intervention.

Prescribed kcal/day from the REE maybe different than the calculated kcal/day goal from the SUPPER Titration. If it is different, enter the new Measured REE kcal/day in the space provided. The SUPPER Titration sheet will utilize this new goal and adjust EN, PN, and Lipid rates accordingly.

At Hour 96 document PINI. This includes albumin, C - reactive protein, fibrinogen, transferrin, and prealbumin.

Discharge and Follow Up

Prior to patient PICU discharge, complete the SUPPER Contact Form with the parent/guardian. This form will be used for the 28 Day Vitals check if patient is not in the hospital or deceased.

There are 5 key sections to the SUPPER Discharge Form, Extubation, PICU Discharge, Hospital Discharge, Early Cessation, and 28 Day Vitals and Patient Death. Complete each of these sections as they occur.

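### The Aim 2 mixed model names AR(1) for unequally spaced samples; a continuous-time structure would deliver the correlation by elapsed time that the SAP describes

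*Combined protocol and SAP*

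**What the plan says.** The Statistical Analysis Plan, Aim 2, first describes a repeated measures ANOVA of the barrier assays with "time (1,2,3,5, and 7 days) as explanatory variables". A mixed model follows on a condition: "If the slope of the serum biomarkers is linear, then change in the slope over time will be calculated". The SAP says that this calculation is to be done "using a linear mixed effects model with an AR(1) variance-covariance structure". If the course is not linear, change-point or nonlinear mixed models replace it.

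The plan gives its reason for the structure: it "allows for measurements taken closer together to be more similar than those farther apart in time, and adjusts the standard errors for this correlation". It does not say whether AR(1) runs on visit order or on elapsed time. It names no random effects and no robust standard errors.

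The sampling tables in the EPN and LPN sections have a row headed "Blood Sample 2mLs" with draws at 0, 12, 24, 48, 72, 96, 120, 144 and 168 hours. Both sections allow 2 hours either side of target. The daily data collection text adds that "SUPPER study labs may be delayed by 1-2 hours, if necessary", so that a draw does not follow a recent vasoactive change. On sample size, Aim 2 states: "With 40 subjects total, we will be able to include up to 4 possible predictors".

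**The concern.** In its standard form, AR(1) sets the correlation between two measurements to rho raised to the number of visits between them. That equals correlation by elapsed time only when visits are equally spaced, and neither time grid in the documents is. The structure named and the property claimed for it therefore do not match.

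The plan relies on this structure to make the standard errors right, and it specifies nothing as a backstop. An analyst who picks the usual AR(1) option and one who codes a continuous-time version would both be following the SAP, yet could report different standard errors and p-values for the same biomarker slope.

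**Working it through.** **Inputs from the documents.** Analysis times are days 1, 2, 3, 5, 7 (gaps 1, 1, 2, 2 days). Blood times are 0, 0.5, 1, 2, 3, 4, 5, 6, 7 days (gaps 0.5, 0.5, then six of 1 day). Total sample is 40. The plan states no standard error, correlation or power for this model, so there is no figure of its own to reproduce.

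**Assumptions.** 20 patients per arm; total variance 1; true correlation phi per day between 0.2 and 0.9; two-sided 5% level; complete data at target times; large-sample normal test.

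**Step 1: correlation pattern.** Take visit-order rho = 0.5 and, for comparison, elapsed-time phi = 0.5 per day.

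| Pair | Days apart | By visit order | By elapsed time |
|---|---|---|---|
| Days 1-2 | 1 | 0.50 | 0.50 |
| Days 1-3 | 2 | 0.25 | 0.25 |
| Days 3-5 | 2 | 0.50 | 0.25 |
| Days 5-7 | 2 | 0.50 | 0.25 |
| Days 1-7 | 6 | 0.0625 | 0.0156 |

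Visit order gives a one-day and a two-day gap the same correlation, and gives two pairs that are both two days apart different ones. The blood schedule does the same: 0-24 h counts as two steps and 24-48 h as one.

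**Step 2: effect on the slope comparison.** Let S have entries phi^|t_i - t_j| (truth) and V have entries rho^|i - j| (working model), with X = [1, t].

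- Fitted rho: the large-sample maximum-likelihood value, which here equals the mean of the adjacent-pair correlations.
- Model variance of the slope difference: (2/20) times the slope element of (X'V⁻¹X)⁻¹.
- True variance: (2/20) times the slope element of (X'V⁻¹X)⁻¹ X'V⁻¹SV⁻¹X (X'V⁻¹X)⁻¹.
- With k = model SE / true SE, type I error = 2[1 - Φ(1.96k)].

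Example, days 1, 2, 3, 5, 7 with phi = 0.5: rho = (0.5 + 0.5 + 0.25 + 0.25)/4 = 0.375. Model SE is 0.0709 and true SE 0.0729, so k = 0.972 (from unrounded values). Type I error = 2[1 - Φ(1.96 × 0.972)] = 5.7%.

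| phi per day | k, days 1,2,3,5,7 | Type I error | k, blood schedule | Type I error |
|---|---|---|---|---|
| 0.2 | 0.992 | 5.2% | 0.970 | 5.7% |
| 0.5 | 0.972 | 5.7% | 0.971 | 5.7% |
| 0.8 | 0.942 | 6.5% | 0.968 | 5.8% |
| 0.9 | 0.929 | 6.9% | 0.964 | 5.9% |

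On days 1, 2, 3, 5, 7 the slope estimate also has up to 6% more variance than under the correct structure (at phi = 0.9). The between-arm mean difference is essentially unaffected on that grid (SE ratio 0.999-1.001).

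**Step 3: does a random intercept change this?** If an intercept carrying 30% of the variance is present and also modelled, the blood-schedule ratio stays at 0.964-0.972 for phi 0.2-0.9.

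**Step 4: other truths on days 1, 2, 3, 5, 7, with AR(1) alone fitted.** With 20% measurement noise left out of the model, the slope ratio is 0.994 at phi 0.2, 1.033 at 0.8, 1.130 at 0.9 and 1.262 at 0.95. With a 30% random intercept left out, it is 1.216 at phi 0.2 and 0.933 at 0.95. Ratios above 1 mean standard errors that are too large.

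**The case against.** The best defence is that the SAP states its intent. Its explanation speaks of separation in time, which fits a continuous-time AR(1), and nothing says that the index is visit order. That stands in part: the documents do not prove that a wrong model will be fitted. But unqualified AR(1) ordinarily means the visit-order form, and the text permits it.

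Second, the day list belongs to the ANOVA sentence, and on the blood schedule six of the eight gaps are 24 hours. This is true, and it is why the effect there is only 3-4%. It does not restore equal spacing.

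Third, visit-order AR(1) still makes correlation fall with distance from any given visit, and at the target times it never ranks a longer separation above a shorter one. That is also right. The fault is in how it treats equal and unequal gaps.

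A reader might go further and infer that AR(1) will make the Aim 2 standard errors too small in general. The documents do not support that. They give no correlation, variance components or random effects, and Step 4 shows that the direction can reverse. Those larger errors come mainly from the omitted component rather than from spacing, but they rule out a general statement on direction. Nor do the documents set a 5% threshold for Aim 2: it appears under Aim 1 only. The model applies only if the course is linear, and Aim 1 describes the trial as a pilot.

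**Conclusion.** The mismatch holds: AR(1) in its standard form does not provide the elapsed-time correlation that the SAP attributes to it, on either time grid in the documents. The numerical consequence is small and conditional. With exponential decay in real time at an assumed 0.2-0.9 per day, and spacing as the only error, slope standard errors are understated by about 1-7% on days 1, 2, 3, 5, 7 and 3-4% on the blood schedule. A test run at a nominal 5% would then have a type I error of about 5.2-6.9% and 5.7-5.9% respectively. Outside those conditions the error can go the other way. This is a minor point, worth correcting because a method that matches the stated aim is available at almost no cost.

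**What to change.** In the Aim 2 plan, replace AR(1) with a continuous-time AR(1) (spatial power or exponential) structure, using each sample's actual hours since time zero. In the same sentence, name the random effects and say whether the model carries a separate measurement-error term; the change of structure alone would not cure the noise problem in Step 4. Actual times also absorb the 2-hour tolerance and the permitted delays.

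The cost is one SAP phrase and one software option. Collection times are already written on the sample labels, so no extra data, patients or procedures are needed.

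I would not use an unstructured covariance instead: nine times need 9 × 10 / 2 = 45 covariance parameters with 40 patients.
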